4. SUBJECT SELECTION

4.1 Inclusion Criteria

In order to participate in this study, a subject MUST:

- Be ≥ 21 and ≤ 90 years of age.
- Provide written informed consent.
- Have endothelial dysfunction defined by impaired flow-mediated vasodilation (FMD $<7\%$).
- Have DM type 2 documented by hemoglobin A1C $\geq 7\%$ or on medical therapy for diabetes.
- Females of childbearing potential must use two forms of birth control for the duration of the study. Female subjects must undergo a serum pregnancy test at screening and within 36 hours prior to infusion.

4.2 Exclusion Criteria

In order to participate in this study, a subject MUST NOT:

- Be younger than 21 years or older than 90 years of age.
- Have a baseline glomerular filtration rate <35 ml/min $1.73m^2$ estimated using the MDRD formula.

- Have an ejection fraction < 45% by gated blood pool scan, two-dimensional echocardiogram, cardiac MRI, cardiac CT or left ventriculogram within the past year, as documented by medical history if history of heart failure.
- Have poorly controlled blood glucose levels with hemoglobin A1C \geq 8.5%.
- Have a history of proliferative retinopathy or severe neuropathy requiring medical treatment.
- Have a hematologic abnormality as evidenced by hematocrit < 25%, white blood cell < 2,500/ μ l or platelet values < 100,000/ μ l without another explanation.
- Have liver dysfunction, as evidenced by enzymes (AST and ALT) greater than three times the ULN.
- Have a bleeding diathesis or coagulopathy (INR > 1.3), cannot be withdrawn from anticoagulation therapy, or will refuse blood transfusions.
- Be an organ transplant recipient or have a history of organ or cell transplant rejection.
- Have a clinical history of malignancy within the past 5 years (i.e., subjects with prior malignancy must be disease free for 5 years), except curatively-treated basal cell or squamous cell carcinoma, or cervical carcinoma.
- Have a condition that limits lifespan to < 1 year.
- Have a history of drug or alcohol abuse within the past 24 months.
- Be on chronic therapy with immunosuppressant medication, such as corticosteroids or TNF α antagonists.
- Be serum positive for HIV, Syphilis – VDRL (Confirmation with FTA-ABS if needed (Syphilis)), hepatitis BsAg, or viremic hepatitis C.
- Be currently participating (or participated within the previous 30 days) in an investigational therapeutic or device trial.
- Be pregnant, nursing, or of childbearing potential while not practicing effective contraceptive methods.
- Any other condition that in the judgment of the Investigator would be a contraindication to enrollment or follow-up.

4.3 Concomitant Treatments, Procedures, and Nondrug Therapies

All concomitant medications (prescription or over-the counter) as well as procedures or nondrug therapies (e.g. continuous positive airway pressure, pulmonary rehabilitation) will be recorded at the initial screening visit and updated at each subsequent visit. Except for other experimental treatments or medications with putative disease modifying effects in endothelial dysfunction, subjects will continue all prior concomitant medications for comorbid diseases to ensure optimal general medical care.

4.4 Withdrawal Criteria

Subjects will be informed that they have the right to withdraw from the study at any time and for any reason without prejudice to future or continued medical care. Subjects must be withdrawn for the following reasons:

- Subject's request.
- Subject is unable or unwilling to comply with the protocol.
- Medical reasons, at the discretion of the investigator.

Reason for withdrawal will be recorded in the subject's case report form. In order to adequately monitor for safety and potential efficacy outcomes, subjects who are withdrawn for any reason after receiving the first infusion should be encouraged to return for all assessments through the end of the study period. All efforts should be made to continue to record safety data and lung function parameters for all withdrawn subjects. Subjects who withdraw for reasons unrelated to the study or study drug (e.g. withdrawal of consent or loss to follow-up) may be replaced if deemed necessary to meet study objectives. Replacement subjects will be assigned unique identification numbers.

5. DONORS

5.1 Normal Donor Eligibility

Donors (male or female) between the ages of ≥ 18 to ≤ 45 (inclusive) will be screened as potential BM donors. Donors will be evaluated by history and physical examination. The history will include:

- History of malignancy
- Bleeding abnormalities
- Prior deep venous thrombosis
- Known cardiac or pulmonary conditions
- Prior blood transfusions
- Vaccinations
- Questions to identify persons at risks of infectious disease transmission, including Zika virus
- Questions to identify persons at risk of transmitting hematological or immunological disease
- A physician will administer the National Marrow Donor Program (NMDP) Questionnaire (a donor health history screening questionnaire).

The physical examination will include review of vital signs and evaluation for potential risks associated with the BM aspiration procedure. Prospective donors will have infectious disease testing including:

- Hepatitis B surface antigen (HBsAg)
- Anti-Hepatitis B core antibody (HBcAb)
- Anti-Hepatitis C virus antibody (HCV Ab)
- Anti-Human Immunodeficiency Virus (HIV) antibody (HIV 1/2)
- Cytomegalovirus antibody (CMV)
- HCV/HIV Nucleic Acid test
- West Nile Virus Nucleic Acid test
- Human T-lymphotropic Virus I/II (HTLV I/II)
- *T. cruzi* ELISA test (Chagas disease)

- *Zika Virus (RNA qualitative Real Time RT-PCR and/or Virus Antibody (IgM), MAC-ELISA)*
- *Rapid Plasma Reagins (RPR) or VDRL (confirmation with FTA-ABS if needed (Syphilis))*

Prospective donors will also have the following blood and urine tests:

- Complete blood count with differential
- Comprehensive metabolic panel, magnesium, calcium, and uric acid
- Urinalysis
- Serum pregnancy test (Female only)

Eligibility Criteria for Normal Donors will include:

- Male and female gender
- No history of malignancy
- No active coagulopathy and/or hypocoagulable state
- No history of cardio/pulmonary conditions
- Negative tests for Hepatitis B Surface Antigen, Hepatitis C antibody, RPR or VDRL, Chagas, HIV 1 and 2 antibody screen, HTLV I and II antibody screen, Zika Virus, and West Nile Virus.
- Hemoglobin \geq 13.0 g/dL if male; and if female donor hemoglobin \geq 11.0 g/dL
- Platelet count 140,000 to 440,000/ul
- WBC 3.0 to 11.0 K/ul
- No anomalies on the CBC and differential suggestive of a hematopoietic disorder
- Creatinine \leq 1.5 mg/dL
- ALT \leq 112 IU/L
- Bilirubin $<$ 1.5 mg/dL
- No diabetes
- Systolic blood pressure \leq 170
- Diastolic blood pressure \leq 90
- No history of autoimmune disorders
- Negative serum pregnancy test for female donors
- Body Mass Index (BMI) \leq 30

Female donors would need to be screened for pregnancy as the procedure may be an added risk to a fetus.

5.2 Donor Consent

Informed consent will be obtained from all potential donors. The procedure will be explained in terms the donor can understand, and will include information about the significant risks of the procedure. Potential donors will have an opportunity to ask questions, the right to refuse or withdraw consent, and access to the results of all tests.

Donors will need to have virology's redrawn if BMA procedure not completed 7 days from the initial virology results.

5.3 Follow-up Schedule for Donors

After discharge from the hospital, the bone marrow donor will be contacted by the study team with a follow-up telephone call. This call will take place approximately 24 hours after leaving the hospital to determine the well-being and health status of the donor. The donor will be provided with contact telephone numbers in the consent form for any questions or comments.

5.4 Biomarker Assessment for Donors

A separate blood sample of about 10mL for gene expression profiling will be obtained at the donation visit. All samples will be identified so that they can be linked to individual subjects. These samples may be stored indefinitely. Individual results will not be returned to the subject or the study physician. The samples will be linked to subjects, but there will be no recontact. A separate genetic consent form will need to be completed for the donors' participation.

Data presented in publications will not contain individual subjects' clinical characteristics or outcomes; only aggregate data from the entire study will be disclosed.

6. TREATMENT OF SUBJECTS

6.1 Study Investigational Product

The investigational product (IP) consists of hMSCs obtained from a healthy donor of bone marrow or from a commercial clinical grade bone marrow source. Screening of allogeneic donors will follow standard transplant practices and all allogeneic donors will meet allogeneic donor eligibility criteria as outlined in 21 CFR Part 1271 and as specified in the POSEIDON-DCM trial (IND #: 14419; NCT01087996). BM will be obtained from normal volunteers and aspirated from the posterior iliac crest. The BM will be aspirated into heparinized syringes. The MNC fraction will be isolated using a density gradient with Lymphocyte Separation Media (specific gravity 1.077). The low-density cells will be collected and washed with Plasma-LyteA containing 1% HSA. The MNCs will be prepared with or without antibiotics. Subjects with a penicillin allergy will not receive antibiotic treated cells. The washed cells will be samples and viable cell numbers determined. The BM MNC will be seeded into 175 cm² tissue culture flasks in alpha MEM containing 20% FBS. After 14 days of culture, passage zero (P0) cells will be harvested by trypsin treatment and expanded into 60 flasks (P1 cells). After 7 to 10 days P1 cells are harvested by trypsin treatment (P1 cells). Cells from P1 will be cultured for 7 to 10 days and harvested by trypsin treatment and expanded into 180 flasks (P2 cells) with the option of

expanding them once again, to P3. After 7-10 days P3 cells would be harvested by trypsin treatment and cryopreserved.

Before dispensing the investigational product, Cell Therapy Lab staff will confirm the CMV status of eligible recipients. This information will be used to select the Allo-hMSC product. CMV status of the recipient and donor of the Allo-hMSC product will be matched. CMV positive or negative Allo-hMSC products may be infused to a CMV positive recipient. All CMV negative recipients will receive CMV negative Allo-hMSC product⁹¹.

6.2 Dosing

The Allo-hMSCs are manufactured by the University of Miami Interdisciplinary Stem Cell Institute, as specified in the POSEIDON-DCM trial (IND #: 14419; NCT01087996).

6.3 Dosage Rationale

A safety profile for IV infusion of hMSCs was based on outcomes from previous completed toxicology results⁸. The results from these previous studies demonstrate that the product can be administered intravenously without toxic events at up to 65×10^6 hMSC/kg dose delivered in one bolus infusion or at 100×10^6 hMSC/kg cumulative dose delivered by 5 infusions (20×10^6 hMSC/kg per infusion).

The evidence supports the conclusion that it is feasible to dose subjects in this study based on a standard dose of hMSCs rather than per kilogram of body weight. The total cell number corresponds to a range of $1.3 - 4.4 \times 10^6$ hMSCs per kg per infusion for subjects with 45kg to 150kg body weight.

In addition, the data from the administration of allogeneic MSCs in the DCM (IND #: 14419; NCT01087996) trial supports the clinical safety of the proposed MSC doses to be administered. Therefore, results from previous trials support the rationale on the safety and potential efficacy of the selected maximum dose of 100×10^6 allo-hMSCs.

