| 
Design and Investigational Plan:
 
To evaluate the role of allogeneic mesenchymal stem cells therapy for endothelial dysfunction in diabetes.
 
Sixteen (16) diabetic subjects with endothelial dysfunction will be scheduled to undergo a peripheral intravenous infusion after meeting all inclusion/exclusion criteria at baseline.
 
PILOT PHASE (Unblinded):
 
The dose for subjects in the pilot phase will vary from 20 million cells to 100 million cells and will be Unblinded, with subjects and study team members aware of the doses administered to the subject. The pilot phase will consist of:
 
Three (3) subjects will be treated with 20 million (20×10^6) allogeneic hMSC's Three (3) subjects will be treated with 100 million (100×10^6) allogeneic hMSC'
 
The three (3) subjects in the low dose group will not be treated less than 5 days apart and will each undergo full evaluation during those five days to show that there are no signs of treatment emergent SAE's (TE-SAE) before continuing with the treatment of further subjects.
 | |

The three (3) subjects in the high dose will not be treated until the three (3) subjects in the low dose have completed their one-month follow-up assessments and safety measures have been reviewed to confirm that there have been no treatment emergent SAE's. In addition, the three (3) subjects in the high dose group will not be treated less than 5 days apart.

Randomized Phase (Double-Blind):

After the pilot phase, subjects will be randomized to one of two treatments in a 1:1 fashion. This phase of the study will be blinded to both subjects and study team members. The randomized phase will consist of ten (10) diabetic subjects with endothelial dysfunction will be subsequently randomized to undergo a peripheral intravenous infusion after meeting all inclusion/exclusion criteria at baseline:

Five (5) subjects will be treated with 20 million (20×10^6) allogeneic hMSC's and Five (5) subjects will be treated with 100 million (100×10^6) allogeneic hMSC's

The Allo-hMSCs will be supplied from an allogeneic human mesenchymal stem cell source or commercial clinical grade bone marrow source manufactured by the University of Miami.

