3. STUDY DESIGN

3.1 Description of the Study

Sixteen (16) diabetic subjects with endothelial dysfunction will be scheduled to undergo a peripheral intravenous infusion after meeting all inclusion/exclusion criteria at baseline. The study will consist of a Pilot Phase and Randomized Phase.

PILOT PHASE

To test the safety of allogeneic mesenchymal stem cells therapy for endothelial dysfunction in diabetes subjects administered via peripheral intravenous infusion, a non-randomized, unblinded pilot phase of six subjects will be performed.

Three (3) subjects will be treated with 20 million (20×10^6) allogeneic hMSCs
Three (3) subjects will be treated with 100 million (100×10^6) allogeneic hMSCs.

The three (3) subjects in the low dose group will not be treated less than 5 days apart and will each undergo full evaluation during those five days to show that there are no signs of treatment emergent SAE's before continuing with the treatment of further subjects.

The three (3) subjects in the high dose will not be treated until the three (3) subjects in the low dose have completed their one-month follow-up assessments and safety measures have been reviewed to confirm that there have been no treatment emergent SAE's. In addition, the first three (3) subjects in the high dose group will not be treated less than 5 days apart.

RANDOMIZED PHASE

After the Pilot Phase, the Randomized Phase will begin. Ten (10) diabetic subjects with endothelial dysfunction will be randomized to undergo a peripheral intravenous infusion in a 1:1 ratio after meeting all inclusion/exclusion criteria at baseline.

Five (5) subjects will be treated with 20 million (20×10^6) allogeneic hMSCs Five (5) subjects will be treated with 100 million (100×10^6) allogeneic hMSCs

The Allo-hMSCs will be supplied from an allogeneic human mesenchymal stem cell source manufactured by the University of Miami.

Electronic randomization will be performed by the University of Miami Biostatistics Collaboration and Consulting Core (BCCC) and communicated to cellular laboratory personnel who have no contact with the investigators or subjects. After each infusion, subjects will be monitored for immediate complications.

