6.4 Administration Rate

Prior clinical trials have used rates up to 30×10^6 hMSC/min where no infusion related toxicity was observed.

In the proposed study, the cell dose to be delivered is 20 million (20×10^6) and 100 million (100×10^6) hMSC/infusion, reconstituted as 0.25 to 1.25 million hMSC/ml, in the following total volume:

80 ml for the 20 million dose (0.5 million hMSC/min)

80 ml for the 100 million dose (2.5 million hMSC/min)

Cells are placed in an 80ml bag and will be delivered at a rate of 2ml/min, and delivered at a maximum rate of 2.5×10^6 hMSC/minute and will last approximately 40 minutes for both doses

The infusion bag will be flushed with an additional 25 ml of 0.9% normal saline at the completion of allo-hMSC infusion and delivered at a rate of 2ml/min.

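### Does the per-kilogram range in the dosage rationale call for a change, given that it matches neither planned dose?

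*Combined protocol and SAP*

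**What the plan says.** Section 6.3 (Dosage Rationale) quotes toxicology results per kilogram: no toxic events at up to 65 × 10^6 cells per kg in a single bolus, or 100 × 10^6 per kg cumulatively over five infusions. It then argues that subjects can be dosed "based on a standard dose of hMSCs rather than per kilogram of body weight" and gives a conversion: "The total cell number corresponds to a range of" 1.3 to 4.4 × 10^6 "hMSCs per kg per infusion for subjects with 45kg to 150kg body weight". The section closes by naming 100 × 10^6 cells as the maximum dose and rests that choice on results from previous trials.

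The planned totals appear in three other places and agree with one another:

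- Synopsis: "The dose for subjects in the pilot phase will vary from 20 million cells to 100 million cells".
- Section 3.1: three pilot subjects at 20 million, then "Three (3) subjects will be treated with 100 million". The randomized phase uses the same two totals, five subjects each.
- Section 6.4: "In the proposed study, the cell dose to be delivered is 20 million", with 100 million as the other level. Each dose is in an 80 ml bag run at 2 ml/min, and the infusion "will last approximately 40 minutes for both doses".

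**The concern.** The toxicology evidence is per kilogram and the study doses are fixed totals. The one sentence that links the two units gives a range that neither total produces. A reader who works backwards from it arrives at about 200 million cells, twice the stated maximum.

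If that total reflected a dose someone intended to give, the dose sections would be in conflict. If the range had been used to set a safety margin, a weight limit or a stopping threshold, the error would carry into the conduct of the trial. The question is therefore whether anything depends on it.

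**Working it through.** **Inputs.** Totals: 20 and 100 million cells (synopsis, Sections 3.1 and 6.4). Weights: 45 and 150 kg (Section 6.3). Stated range: 1.3 to 4.4 × 10^6 per kg (Section 6.3). Toxicology figure: 65 × 10^6 per kg in one bolus (Section 6.3). All results per kg below are in millions of cells.

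**1. Attempt to reproduce the stated range.** Cells per kg = total ÷ weight. The heaviest subject gives the lower end and the lightest the upper end.

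| Total (million) | ÷ 150 kg | ÷ 45 kg |
|---|---|---|
| 20 | 0.133 | 0.444 |
| 100 | 0.667 | 2.222 |
| Stated | 1.3 | 4.4 |

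Neither total reproduces it. Compared with 100 million, the stated ends are 1.3 ÷ 0.667 = 1.95 and 4.4 ÷ 2.222 = 1.98 times too large. Compared with 20 million, they are 1.3 ÷ 0.133 = 9.8 and 4.4 ÷ 0.444 = 9.9 times too large.

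**2. Try other readings.**

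- Both doses in one span: 20 ÷ 150 = 0.13 to 100 ÷ 45 = 2.22. No match.
- The two doses added, 120 million: 120 ÷ 150 = 0.80 to 120 ÷ 45 = 2.67. No match.
- Weights taken as pounds (1 lb = 0.4536 kg): 1.47 to 4.90 for 100 million and 0.29 to 0.98 for 20 million. No match.

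**3. Solve backwards for the total.** 1.3 × 150 = 195 million and 4.4 × 45 = 198 million. If the printed figures were rounded to nearest, the lower end allows 1.25 × 150 = 187.5 to 1.35 × 150 = 202.5, and the upper end 4.35 × 45 = 195.75 to 4.45 × 45 = 200.25. If they were truncated, the intervals are 195 to 210 and 198 to 202.5. Either way the sentence supports a total of about 200 million and no finer statement. The digits also equal the 20 million range with the decimal point moved one place. The documents do not show which explanation applies.

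**4. Check Section 6.4 against itself.** Concentration: 20 ÷ 80 = 0.25 and 100 ÷ 80 = 1.25 million/ml. Duration: 80 ml ÷ 2 ml/min = 40 min. Rate: 0.25 × 2 = 0.5 and 1.25 × 2 = 2.5 million/min. Back to totals: 0.5 × 40 = 20 and 2.5 × 40 = 100 million. All agree with what the section prints, so the inconsistency is confined to the one sentence in Section 6.3.

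**5. Overlap with the stated range.** At 100 million, a subject reaches 1.3 million/kg at 100 ÷ 1.3 = 76.9 kg, so subjects of 45 to about 77 kg fall inside the range and heavier ones fall below it. At 20 million the weight would have to be 20 ÷ 1.3 = 15.4 kg or less, so no subject of 45 to 150 kg falls inside it.

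**6. Effect on the toxicology comparison.** Using the upper end of each range: 65 ÷ 4.4 = 14.8 as printed, 65 ÷ 2.222 = 29.3 for 100 million, and 65 ÷ 0.444 = 146 for 20 million. The ratio stays large in every case, and the printed range gives the smallest one.

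**7. Where the range is used.** Sections 4.1 and 4.2 set no weight limit. Section 6.4 and Appendix 1 run the infusion at a fixed 2 ml/min whatever the weight. The stopping guidelines in Section 9.2.4 and Appendix 1 rest on events, symptoms and oxygen saturation. Section 10 has no weight-based or per-kilogram analysis. The range is used nowhere outside Section 6.3.

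**The case for a change.** The best case for acting is that this is a two- to tenfold numerical error in the safety rationale of an early-phase dose study. It sits in the only sentence that puts the study doses in the unit of the toxicology data. Section 11.4.2 asks the DSMB to evaluate protocols for safety, and the board should receive a rationale that agrees with the doses. No lenient reading removes the problem. A misprinted exponent (10^5 in place of 10^6) would make the range right for 20 million cells, but would leave the maximum dose with no per-kg figure. If the range belongs to another product or trial, the text does not say so, and the preceding sentence is about subjects in this study. The correction would cost one sentence.

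The arithmetic in that argument stands in full. What does not follow is that the trial is affected. The section's conclusion on the maximum dose is drawn from previous trials, and the comparison with 65 × 10^6 per kg points the same way under any of the three ranges. It would also be too strong to say that the range fits no one in the study, since part of the high-dose weight range falls inside it.

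**Conclusion.** The inconsistency is genuine, and it is clerical. If the 20 and 100 million totals are as intended, Section 6.3 overstates exposure per kg about tenfold for the low dose and about twofold for the high dose. That assumption rests on the agreement of the synopsis with Sections 3.1 and 6.4, and on the exact internal arithmetic of Section 6.4. The source of the slip, a total near 200 million or a shifted decimal, cannot be settled from the documents.

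No change to the plan follows. Doses are fixed totals, so the range does not determine what any subject receives. No eligibility, conduct, stopping or analysis rule refers to it, and the toxicology comparison is not reversed. Correcting the sentence would change nothing the trial does or concludes. The sponsor must still reconcile Section 6.3 with the synopsis and Sections 3.1 and 6.4. That is low-priority housekeeping of the text, and this note takes no position on which figure is right.
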